#### *5.3.1.1 Adverse Events*

Investigators will record data related to AEs, including duration, severity, relationship to study drug, action(s) taken, and outcome throughout this clinical trial. The Investigator will assess the severity of each AE according to the National Cancer Institute CTCAE version 5.0 (CTCAE 2017), summarized in Table 5 of the study protocol version 5.0. All AEs occurring in all subjects will be documented following signing of the first informed consent until approximately 30 days after the last study treatment (Follow-up Visit).

#### *5.3.1.2 Physical Examinations*

A full physical examination will include assessments of the cardiovascular, respiratory, abdomen, neurological, and musculoskeletal systems; head, eyes, ears, neck, and throat (HEENT); thyroid; skin; and extremities. The full physical examination may exclude rectal, genitourinary, and breast exams.

An abbreviated/directed physical examination includes the following components: cardiovascular, respiratory, abdomen, and any other systems indicated by history or clinical judgement.

A full physical examination will be performed during the Day 1 and Week 12 visits. Abbreviated physical examinations will be performed at Screening, Week 2, Week 4, Week 8, and Safety Follow-up visits as shown in [Table 8](#), [Table 9](#), [Table 10](#), and [Table 11](#).

#### *5.3.1.3 Vital Signs*

The following vital signs will be assessed: blood pressure (systolic and diastolic; mmHg); pulse rate (beats per minute); respiration rate (breaths per minute); and body temperature (°C). Vital signs will be obtained at all clinic visits as shown in [Table 8](#), [Table 9](#), [Table 10](#), and [Table 11](#).

Total body weight (kg) will be collected at each visit. Height (cm) will be measured at Screening and every 6 months thereafter (for those enrolled in the extension). From these assessments, body mass index (BMI; kg/m^2) and body surface area (BSA; m^2) will be calculated.

#### *5.3.1.4 Body Weight and Height*

Total body weight (actual body weight) will be measured at every visit using a calibrated balance. Height needs to be recorded at Screening and every 6 months thereafter (for those enrolled in the extension). Body mass index (BMI) and body surface area (BSA) will be calculated using the most recent of these measurements. In the extension period, height will need to be updated, as growth dictates changes in BSA and therefore GC dose. The most recent height and weight values will be used when BMI and BSA are reported during the extension period.

#### *5.3.1.5 Electrocardiograms*

All 12-lead ECG assessments will include: heart rate, RR, PR, QRS, QT, and QTc intervals, preferably using Fridericia's formula. ECGs will be performed at Screening, Day 1 (pre-dose), Week 2, Week 12, and Safety Follow-up visits as shown in [Table 8](#) and [Table 10](#).

#### *5.3.1.6 Clinical Laboratory and Urinalysis*

Fasting is not required for laboratory assessments. Clinical laboratory assessments include coagulation panel (Screening only), hematology, chemistry (including liver function tests AST, ALT, ALT, gamma-glutamyl transferase [GGT], total and direct bilirubin, and total bile acids), and thyroid panel ([Table 12](#)). eGFR for Screening and throughout the trial will be calculated from blood creatinine measured as part of Screening clinical chemistry utilizing the creatinine-based Schwartz equation.

Clinically significant laboratory findings are those that are not associated with the underlying disease, unless judged by the Investigator to be more severe than expected for the subject's condition. All laboratory tests with values considered clinically significantly during the Treatment Period or within 30 days after the last dose of study drug should be reported as AEs and repeated at least weekly until the values return to normal or baseline or are no longer considered clinically significant by the Investigator or MM. If such values do not return to normal/baseline within a period judged reasonable by the Investigator, the etiology should be identified, and the Sponsor notified.

Clinical lab assessments will be performed at all clinic visits as shown in [Table 8](#), [Table 9](#), [Table 10](#), and [Table 11](#); a complete list of clinical laboratory tests is found in Appendix 6 of study protocol version 5.0.

#### *5.3.1.7 Psychiatric Evaluations*

Subjects will be monitored for depression and anxiety during the study using the Patient Reported Outcomes Measurement Information System (PROMIS) Pediatric SF (Short Form) v2.0, the PROMIS Parent-Proxy SF (Short Form) v2.0, or the Survey of Well-Being of Young Children (SWYC). The questionnaire used will depend upon the subject's age. Any subject who

develops severe depression or anxiety (CTCAE Grade 3 or higher), as assessed by the Investigator, will require study drug discontinuation and appropriate follow-up. The Columbia–Suicide Severity Rating Scale will be used during the study to monitor suicidal ideation and behavior for subjects aged 6 to 17 years old. The Baseline/Screening Version of the C-SSRS, which assesses both lifetime history and history from the last 12 months, will be used at the Screening Visit to determine subject eligibility. The Since Last Visit Version of the C-SSRS will be used at all subsequent visits (Week 2, Week 4, Week 8, and Week 12) as specified in [Table 8](#), [Table 9](#), [Table 10](#), and [Table 11](#).

#### *5.3.1.7.1 Depression Assessment*

PROMIS SF v2.0 or the PROMIS Parent-Proxy SF v2.0 will be used to monitor depression and anxiety in subjects aged 5 to 17 years old. The SWYC will be used to monitor depression and anxiety in subjects under 5 years of age. These evaluations will be conducted at Screening, Week 2, Week 4, Week 8, Week 12, and Safety Follow-up visits as shown in [Table 8](#), [Table 9](#), [Table 10](#), and [Table 11](#).

#### *5.3.1.7.2 Anxiety Assessment*

The PROMIS Pediatric Anxiety SF v2.0 and the PROMIS Parent Proxy Anxiety SF v2.0 will be used during the study to monitor subjects for anxiety. The Pediatric version is self-administered and the PROMIS Parent Proxy SF v2.0 is completed by the parent of a child in the study to assess for symptoms of anxiety. The assessment consists of 8 items using a multiple-choice response format and will be used at screening and all subsequent visits specified.

Refer to Section 6.1.6 of the study protocol version 5.0 for depression and/or anxiety individual treatment-stopping criteria.

#### *5.3.1.7.3 Survey of Well-Being of Young Children*

The SWYC is a brief questionnaire (completed by parents) that assesses the following 3 categories of well-being in children 2 to 4 years of age: developmental, emotional/behavioral, and family. Refer to Section 6.1.6 of the study protocol version 5.0 for depression and/or anxiety individual treatment-stopping criteria.

#### *5.3.1.8 Dose Limiting Toxicity*

A Dose Limiting Toxicity (DLT) is defined as a Common Terminology Criteria for Adverse Events (CTCAE) Grade 3 or higher treatment-emergent adverse event (TEAE) considered at least possibly related to study drug. If a subject experiences a DLT, study drug will be discontinued. DLTs are clinically significant AEs (see Protocol 5.0 Section 6.1.7). If 2 subjects in a cohort meet individual stopping criteria, the entire cohort will be stopped or dose-reduced.

### *5.3.2 Pharmacokinetic and Pharmacodynamic Assessments*

PD hormone assessments adrenocorticotrophic hormone (ACTH), 17-hydroxyprogesterone (17OHP), A4, and testosterone (T) will be collected Day 1, Week 2, Week 4, Week 8, and Week 12 as shown in [Table 8](#), [Table 9](#), [Table 10](#), and [Table 11](#).

## 6 STUDY OBJECTIVES AND ENDPOINTS

SPR001-205 is the first study of tildacerfont in children and will be used to assess safety and to determine the consistency of preliminary tildacerfont PK in pediatric subjects. The primary objective is to gain knowledge of the safety profile of tildacerfont. The secondary objectives of the study determine the consistency of tildacerfont PK in children with the current PBPK model and characterize the efficacy of tildacerfont in reducing androgen levels and reducing GC dosing based on A4 normalization over 12 weeks of treatment. Exploratory objectives include characterizing biomarker outcomes of ACTH, 17-OHP, A4, and T ([Table 3](#)).

An optional extension period will provide additional open-label treatment with tildacerfont to provide long-term safety data for up to two years.

### 6.1 Objectives and Endpoints

#### 6.1.1 Primary

The primary objective is to evaluate the safety of tildacerfont in pediatric (ages 2 to 17 years old) and adult subjects ( $\geq 18$  years old) with classic congenital adrenal hyperplasia. The primary endpoint is the occurrence of AEs and SAEs as described in [Section 5.3.1.1](#).

#### 6.1.2 Secondary

Secondary objectives for Cohorts 1-3 are to characterize the efficacy of tildacerfont in reducing A4 levels after 4 and 12 weeks of treatment and reducing GC dosing after 12 weeks of treatment. The associated secondary endpoints are the proportion of subjects with a reduction from baseline in A4 or a reduction in GC dosing at Week 12; and the proportion of subjects elevated baseline A4 (baseline A4  $>$  ULN) who achieve a reduction in A4 at Week 4 or who achieve normalization of A4 at Week 4 or Week 12.

Secondary objectives for Cohorts 4-9 are to characterize the efficacy of tildacerfont in reducing A4 levels after 4 weeks of treatment. The associated secondary endpoints are the proportion of subjects with a reduction from baseline in A4 or normalization of A4 at Week 4.

#### 6.1.3 Exploratory

Exploratory objectives include characterizing biomarker outcomes of ACTH, 17-OHP, A4, and T over the 12-week Treatment Period. The exploratory endpoints are outlined in [Table 4](#) below.

**Table 3 Objectives and Endpoints**

Cohorts 1-3 (12-week Treatment)			
	Objective	Endpoint	Section Number
1.	Primary		
1.1.	To evaluate the safety of tildacerfont in pediatric subjects with CAH	AEs and SAEs	14.1
2.	Secondary		
2.1.	To determine the efficacy of tildacerfont on disease control or reduction of GC use in subjects with classic CAH during 12 weeks of treatment	Proportion of subjects who achieve a reduction in A4 or reduction in GC dosing during treatment period	13.1.1
2.2.	To determine the efficacy of tildacerfont on disease control in subjects with classic CAH after 4 or 12 weeks of treatment	
 
• Proportion of subjects with elevated baseline A4 who achieve a reduction in A4 at Week 4
 
• Proportion of subjects with elevated baseline A4 who achieve A4 normalization at Week 4 or Week 12
 
	13.1.2
2.3.	To determine the consistency of preliminary tildacerfont PK in subjects with those simulated in a PBPK model	Tildacerfont plasma concentrations will be compared with the current PBPK simulation for consistency	Provided in a separate SAP
3.	Exploratory		
3.1.	To explore changes in PD biomarkers in pediatric subjects with CAH	Change from baseline in adrenocorticotrophic hormone (ACTH), 17hydroxyprogesterone (17-OHP), A4, and testosterone	13.2.1
COHORTS 4, 5, 6, 8, 7, and 9 (4-week Treatment)			
4.	Primary		
4.1	To evaluate the safety of tildacerfont in subjects with CAH	Adverse events (AEs) and serious adverse events (SAEs)	14.1
5.	Secondary		
5.1	To determine the efficacy of tildacerfont on disease control in subjects with classic CAH after 4 weeks of treatment	
 
• Proportion of subjects who achieve reduction in androstenedione (A4) at Week 4
 
• Proportion of patients who achieve A4 normalization at Week 4.
 
	13.1.1
5.2	To determine the consistency of preliminary tildacerfont pharmacokinetics (PK) in subjects with those simulated in a physiologically based PK (PBPK) model	Tildacerfont plasma concentrations will be compared with the current PBPK simulation for consistency	Provided in a separate SAP
6.	Exploratory		
6.1	To explore changes in pharmacodynamic (PD) biomarkers in subjects with CAH	Change from baseline in adrenocorticotrophic hormone (ACTH), 17hydroxyprogesterone (17-OHP), A4, testosterone	13.2.1

EXTENSION (Cohorts 1-9)			
7.	Primary		
7.1	To evaluate the safety of tildacerfont in subjects with CAH	AEs and SAEs	14.1
8.	Secondary		
8.1	To determine the efficacy of tildacerfont on reduction of glucocorticoid (GC) use in subjects with classic CAH after 4 weeks or 12 weeks of treatment	

• Proportion of subjects who achieve reduction in glucocorticoid (GC) dosing (beyond 12 weeks for Cohorts 1-3 and beyond 4 weeks for Cohorts 4-9)

• Proportion of subjects who achieve approximately physiologic GC dosing (<math>\leq 11 \text{ g/m}^2/\text{d}</math>)

	13.1.1
8.2	To determine the efficacy of tildacerfont on disease control in subjects with classic CAH	

• Proportion of subjects with elevated A4 at completion of treatment period (Week 12 for Cohorts 1-3 and Week 4 for Cohorts 4-9) who achieve a reduction in A4.

• Proportion of subjects with elevated A4 at completion of treatment period who achieve A4 normalization

	13.1.2
9.	Exploratory		
9.1	To explore changes in pharmacodynamic (PD) biomarkers in pediatric subjects with CAH	Change from baseline in adrenocorticotropic hormone (ACTH), 17-hydroxyprogesterone (17-OHP), A4, testosterone, (at Week 4 for all cohorts and Week 12 for Cohorts 1-3)	13.2.1
9.2	To explore the impact of tildacerfont on skeletal maturation	Change from baseline in predicted adult height	5.3.1.4

**Table 4** Detailed Exploratory Objectives and Endpoints

Objective		Endpoint	Section Number
1. Change from baseline over 12 weeks			
1.1.	To explore changes from baseline in pharmacodynamic (PD) biomarkers in pediatric subjects with CAH over 12 weeks	Log-transformed change from baseline in ACTH	13.2.1
1.2.		Log-transformed change from baseline in 17-OHP	13.2.1
1.3.		Log-transformed change from baseline in A4	13.2.1
1.4.		Log-transformed change from baseline in T, by sex	13.2.1
2. Change from baseline in ratios over 12 weeks			
2.1.	To explore changes in select PD biomarkers ratios in pediatric subjects with CAH over 12 weeks	Change from baseline in A4/T ratio (males only)	13.2.2
3. Proportion of subjects with reduction [1] overall and [2] by subgroup (Baseline A4 ≤ ULN; Baseline A4 > ULN) [3] by subgroup (Male; Female)			
3.1.	To explore the proportion of subjects with changes in PD biomarkers at Week 4, Week 8, and Week 12	ACTH [a] any reduction; [b] ≥ 50% reduction; [c] ≤ ULN	13.2.3
3.2.		17-OHP [a] any reduction; [b] ≥ 50% reduction; [c] ≤ ULN	13.2.3
3.3.		A4 [a] any reduction; [b] ≥ 50% reduction; [c] ≤ ULN	13.2.3
3.4.		Testosterone by sex [a] any reduction; [b] ≥ 50% reduction; [c] ≤ ULN	13.2.3
4. Change from baseline in GC total daily dose at Week 12			
4.1.	To explore changes in GC total daily dose at Week 12	Change from baseline (mg)	13.2.4
4.2.		Change from baseline adjusted for body surface area (mg/m  )	13.2.4
4.3.		Percent change from baseline	13.2.4
4.4.		Proportion of subjects with GC reduction	13.2.4
4.5.		Proportion of subjects who decrease frequency of administration	13.2.4

## 7 SAMPLE SIZE AND POWER

No formal sample size calculation was performed. A sample size of up to approximately 55 children (i.e., 30 children 11- to 17-years of age, and 25 children 2- to 10-years), will provide adequate data to assess the initial safety of tildacerfont in a pediatric population and provide data to support the continued use of the PBPK model to determine pediatric dosing requirements in future studies. Although this is a pediatric study, up to 15 adults are included in this study to allow for all new dosing regimens to be tested in adults prior to children. The safety profile of tildacerfont in adults will primarily be established in other studies.

The study is expected to enroll approximately 20 children across the first 3 cohorts (i.e., Cohorts 1, 2, and 3), 10 in the 11-to 17- year age group and 10 in the 2-to 10- year age group. If the optional Cohort 1a is initiated (up to 5 subjects), however, Cohorts 1 to 3 may enroll up to 25 children total, 15 in the 11-to 17-year-old age group and 10 in the 2-to 10-year-old age group. Up to an additional six cohorts (Cohorts 4-9) are planned to investigate BID dosing over 4 weeks of treatment. The study will also enroll up to approximately 15 adults aged  $\geq 18$  years across Cohorts 4 and 5; and up to approximately 30 children across 4 additional cohorts [up to 15 in the 11- to 17-year age group (Cohorts 6 and 8) and up to 15 in the 2- to 10-year age group (Cohorts 7 and 9)]. If all possible doses are studied, total sample size of this study may be up to approximately 55 children and 15 adults. Up to a total 70 subjects will be enrolled in the study. Please see [Table 1](#) for subject numbers by dosing cohort:

## 8 ANALYSIS SETS

The Safety (SAF) Analysis Set is defined as all subjects who receive at least one dose of study drug. This will be the primary analysis set for general and safety analyses.

The Pharmacokinetic (PK) Analysis Set will include all subjects in the Safety Analysis Set with at least one post-dose PK sample above the limit of quantification.

The Pharmacodynamic (PD) Analysis Set will include all subjects in the Safety Analysis Set with a baseline A4 assessment or GC dose and at least one evaluable post-baseline A4 assessment.

The Elevated Baseline Pharmacodynamic (EBPD) Analysis Set will include all subjects in the PD analysis set whose baseline A4 assessment is greater than the upper limit of normal.

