8.2. Populations for Analyses

The Safety Population will include all participants who receive at least 1 dose of study drug and will be the primary analysis set for general and safety analyses.

The PK Population will include all participants in the Safety Population with at least 1 post-dose sample above the limit of quantification.

The PD Population will include all participants in the Safety Population with at least 1 evaluable post-baseline PD assessment.

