### 13.1 Secondary Efficacy Analysis

The secondary “treatment policy” estimands are evaluated by two secondary efficacy assessments.

#### 13.1.1 Reduction in A4 or Reduction in GC Dosing at Week 12

Population: The analysis population for the secondary efficacy analyses is the PD analysis set.

Variable: The analysis variable is the proportion of subjects in the PD analysis set who are responders (defined in [Table 5](#)). This proportion is calculated for each cohort as the number of subjects at Week 12 (at Week 4 for cohorts 4 through 9) who have a reduction of A4 or reduction in GC reduction, divided by the total number of subjects in the PD analysis who were enrolled in each cohort. This proportion is also calculated to evaluate the overall subjects at Week 12 (at Week 4 for cohorts 4 through 9) by pooling the responders and dividing by the total number of subjects in the PD analysis set.

Subjects with missing A4 or GC dosing information at a given visit are assumed to be non-responders at that visit. Subjects who do not have a reduction from baseline in A4 or a reduction in GC dose are considered non-responders.

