### *13.1.2 Elevated Baseline A4 who Achieve a Reduction in A4 at Week 4*

Population: The analysis population for the secondary efficacy analyses is the EBPD analysis set.

Variable: The analysis variable is the proportion of subjects in the EBPD analysis set who are responders (defined in [Table 5](#)). This proportion is calculated for each cohort as the number of subjects at Week 4 who have a reduction of A4, divided by the total number of subjects in the EBPD analysis who were enrolled in each cohort.

Subjects with missing data at a given visit are assumed to be non-responders at that specific visit. Subjects who do not have a reduction from baseline in A4 are considered non-responders.

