## 15 CHANGES RELATIVE TO THE PROTOCOL-SPECIFIED ANALYSIS

Study Protocol Section 8.2 defines the PD population as including “all subjects in the Safety Population with at least 1 evaluable post-baseline PD assessment.” Given the vague language in the protocol of how to determine eligibility for the PD population – if for example a subject must have a non-missing post-baseline from all six hormones (ACTH, 17-OHP, A4, testosterone, and 11KT), of any of the six PD hormones, or one specific hormone, the SAP added the specificity that the PD population includes “all subjects in the Safety Analysis Set with a baseline A4 assessment and at least one evaluable post-baseline PD A4 assessment” to align with the A4-dependent secondary efficacy analyses.

SAP [Section 8](#) additionally defines the Elevated Baseline Pharmacodynamic Analysis Set to support the secondary efficacy analysis of subjects with elevated baseline A4 who achieve a reduction in A4 at Week 4.

The Study Protocol Section 8.3.6 specifies that the hormone, 11-ketotestosterone (11-KT), will be summarized as part of the pharmacodynamic analyses, including: general summary statistics by visit, 11-KT/T ratio summaries by visit for males and females; and proportion of subjects with any reduction in 11-KT, a  $\geq 50\%$  reduction in 11-KT, and a normalization of 11-KT ( $11\text{-KT} \leq \text{ULN}$ ). 11-KT assessments, however, will not be provided to Spruce for this study. There are no standard assay or normal references of 11-KT for children. In addition, developing and validating an assay could not be completed in time for this study. Therefore, any protocol specified pharmacodynamic and exploratory endpoints for 11-KT will not be performed.

The Study Protocol Section 8.3.6 mentions that exploratory endpoint of the proportion of subjects with baseline dosing  $> 3 \times$  daily who decrease frequency of administration  $\leq 3 \times$  daily. Given that the dose frequency is collected in a free text form in the Concomitant Medication eCRF form, the dose frequencies are not standardized and easily analyzable, therefore GC medications will only be listed and not summarized to provide information supporting this exploratory endpoint.

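### SAP Sections 8 and 15 define the PD set differently for the composite endpoint, and both versions drop dosed subjects with no post-baseline A4 from responder denominators meant to count missing data as non-response

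*SAP*

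**What the plan says.** The protocol's definition is broad: "The PD Population will include all participants in the Safety Population with at least 1 evaluable post-baseline PD assessment" (Protocol 8.2). The SAP narrows it to androstenedione (A4), in two versions.

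- SAP 8 takes from the Safety set those subjects "with a baseline A4 assessment or GC dose and at least one evaluable post-baseline A4 assessment".
- SAP 15, which explains the departure from the protocol, describes the same set as "all subjects in the Safety Analysis Set with a baseline A4 assessment and at least one evaluable post-baseline PD A4 assessment".

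The two secondary responder endpoints use this set as follows.

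- The composite (SAP 13.1.1) is the number of responders "divided by the total number of subjects in the PD analysis who were enrolled in each cohort".
- The elevated-A4 endpoint (SAP 13.1.2) uses the EBPD set, which "will include all subjects in the PD analysis set whose baseline A4 assessment is greater than the upper limit of normal" (SAP 8).

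For missing data, SAP Table 5 scores every responder variable 0 when the value is missing. Section 13.1.1 has a matching rule, and Section 13.1.2 states: "Subjects with missing data at a given visit are assumed to be non-responders at that specific visit". Section 13.1 says that the secondary treatment-policy "estimands are evaluated by two secondary efficacy assessments".

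**The concern.** There are two separate problems.

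First, one named set has two membership rules. SAP 4 ranks the SAP above the protocol, but nothing ranks Section 8 above Section 15. A subject with a GC dose and a post-baseline A4 but no baseline A4 is in the set under Section 8 and out of it under Section 15.

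Second, both rules require a post-baseline A4. A subject who gives a Week 2 sample and then leaves stays in the denominator and counts as a failure at Week 4 or Week 12. A subject who leaves with no post-baseline A4 is not counted at all. Early exits may be related to treatment, because the stopping criteria in Protocol 6.1 require study drug to be discontinued. Discretionary replacement (Protocol 6.1 and 6.2) could make the loss harder to see.

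At stake are the cohort-level and overall response rates and their exact intervals. The primary safety endpoint uses the Safety set and is not affected.

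**Working it through.** **Which endpoint each problem reaches**

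| Subject (dosed) | Composite, Section 8 | Composite, Section 15 | Elevated-A4 (EBPD) |
|---|---|---|---|
| GC dose and post-baseline A4, no baseline A4 | in | out | out under either |
| Baseline A4 above ULN, some post-baseline A4, target visit missed | in, non-responder | in, non-responder | in, non-responder |
| Baseline A4 above ULN, no post-baseline A4 | out | out | out |

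The first row concerns only the composite. The third row concerns both endpoints. Section 8 could also be parsed as a baseline A4 alone, or else a GC dose together with a post-baseline A4. That reading would keep the third-row subject, but Section 15 points the other way.

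**When a baseline A4 could be missing.** SAP 9.4.9 averages A4 from Screening to Day 1. In Cohorts 1-3 the schedule starts PD sampling on Day 1, and the screening laboratory footnote does not list A4 (Protocol Appendix 1). A missed Day 1 draw could then leave no baseline. In Cohorts 4-9, A4 is a screening laboratory test (Appendix 3) and inclusion criterion 4 sets a range for it, so the case should be rare.

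**Size of the definition mismatch** (responder counts assumed; one subject without baseline A4)

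- 3/5 = 60.0% under Section 8 becomes, under Section 15, 3/4 = 75.0% if that subject was a non-responder, or 2/4 = 50.0% if a responder through GC reduction.
- 6/10 = 60.0% becomes 6/9 = 66.7% or 5/9 = 55.6%.

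The shift can go either way.

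**Size of the post-baseline requirement.** The plan states no figure to reproduce: SAP 7 reports no formal sample size calculation, and no dropout rate is given. Cohort sizes come from SAP Table 1: 5 in Cohorts 1, 1a and 2, and 10 in Cohort 3, so the planned maximum for Cohorts 1-3 is 5 + 5 + 5 + 10 = 25. With r responders among N dosed and one subject lost who would have been scored a non-responder:

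shift = r/(N − 1) − r/N = r/[N(N − 1)]

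- N = 5, r = 2 to 4: 2/20 to 4/20, or 10 to 20 points.
- N = 10, r = 5 to 8: 5/90 to 8/90, or 5.6 to 8.9 points.
- N = 25, r = 12 to 20: 12/600 to 20/600, or 2.0 to 3.3 points.

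Examples with Clopper-Pearson 95% intervals, the method in SAP 13.1.1.1:

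| N dosed | Lost subject excluded | Lost subject = non-responder |
|---|---|---|
| 5 | 3/4 = 75.0% (19.4 to 99.4) | 3/5 = 60.0% (14.7 to 94.7) |
| 5 | 4/4 = 100% (39.8 to 100) | 4/5 = 80.0% (28.4 to 99.5) |
| 10 | 6/9 = 66.7% (29.9 to 92.5) | 6/10 = 60.0% (26.2 to 87.8) |
| 25 | 15/24 = 62.5% (40.6 to 81.2) | 15/25 = 60.0% (38.7 to 78.9) |

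For the elevated-A4 endpoint, N is the number of dosed subjects with baseline A4 above ULN, which may be smaller than the cohort.

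**The case against.** The strongest reply is that few subjects will lack a post-baseline A4.

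- **Early Termination visit.** Protocol 3.1.2.8 includes an A4 draw. Protocol 6.1 requires this visit to be scheduled when study drug is stopped, and 6.2 asks for it, if possible, after any dosed withdrawal.
- **Day 1 post-dose samples.** All cohorts except Cohort 3 have A4 drawn 0.5 to 1.5 and 3 to 5 hours after the first dose, although children aged 2 to 10 may decline serial sampling. If these samples count, almost every dosed subject in those cohorts qualifies on Day 1.

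This limits how often the problem arises but does not remove it. The SAP does not define evaluable, and SAP 9.4.9 leaves it unclear whether Day 1 post-dose values enter the baseline mean. Cohort 3, with a single pre-dose Day 1 sample, is the most exposed.

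It can also be said that the missing-data rule works visit by visit within a set and does not decide membership, that a treatment-policy label does not fix the set either, and that the protocol already required a post-baseline PD value. These points are fair, so the texts do not strictly contradict each other. The result is still that the subjects with the least data escape a rule meant to count missing data as failure.

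Finally, SAP 11.1 plans a listing of PD-set exclusions with reasons. That makes the loss visible but does not correct the reported rates.

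**Conclusion.** The concern holds, within limits. The Section 8 and 15 definitions differ, and the difference can move the composite rate in either direction. The shared post-baseline requirement removes dosed subjects with no post-baseline A4 from both responder denominators. If the lost subject would have been a non-responder and there is at least one responder, the rate can only rise: about 10 to 20 points per lost subject in a cohort of 5, 6 to 9 in a cohort of 10, and 2 to 3 in a pooled 25. These sizes rest on assumed responder counts and one lost subject. The documents do not show how many such subjects to expect.

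A reader might infer three stronger things that the documents do not support.

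- That the mismatch undermines both secondary endpoints. It does not: the EBPD set needs a baseline A4 above ULN under either definition.
- That early dropouts in general are removed. Only those with no post-baseline A4 at all are removed, and an Early Termination draw would keep many.
- That a 20-point inflation is typical. It is the top of the illustrated range for one lost subject in a cohort of 5. The cohorts planned at 5 all have serial Day 1 sampling, so the figure for a cohort of 10 fits the most exposed cohort better.

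The endpoints are secondary and descriptive in an exploratory, uncontrolled study. This is a worthwhile correction, not a threat to the study's primary purpose.

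**What to change.** 1. Put one PD-set definition, word for word, in SAP 8 and SAP 15, with the and/or logic made explicit.
2. Define evaluable, and state whether Day 1 post-dose A4 counts as post-baseline.
3. For the composite, use all dosed subjects as the denominator. Requiring a baseline A4 here would be wrong, because Table 5 lets a subject respond through GC reduction alone.
4. For the elevated-A4 endpoint, use all dosed subjects with baseline A4 above ULN.
5. For both, score missing as non-response. For the composite, say how a subject with one component missing and a GC reduction recorded is scored.
6. Keep the PD set for continuous biomarker summaries.

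If the present denominators are kept, state that the rates are conditional on having a post-baseline A4, and report the number excluded by cohort beside each rate.

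The cost is SAP wording and matching programming, with no new data. Reported response rates may be slightly less favourable.
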